12.2 Follow-up

Follow-up assessments will be carried out at 3 months (+/- 1 month window) and 6 months (+/- 2month window) by either telephone or email, with both used where possible to maximise response. Alternatively, if participants are unwilling or unable to complete their follow up over the telephone or by email, they will be asked if they would be willing to fill out the follow up questionnaires sent to them in the post. A freepost self-addressed envelope will be provided. Around 3 attempts will be made to contact the participant at each follow-up. If it is not possible to contact participants, a relative/carer may be contacted as an alternative. If all contact attempts are unsuccessful, a questionnaire booklet may be posted to the participant for them to complete and return. If a routine in-person outpatient visit is scheduled for clinical reasons within the follow-up visit windows, the follow up questionnaires may be completed in-person, and/or clinical information collected at this visit may be used for followup assessments. Site staff will ensure, to the best of their knowledge, that participants are still alive before any contact attempts are made, by checking all local patient management systems available to them e.g. Spine data (England), Welsh Clinical Portal (Wales).

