11.9 Compliance

Pls and other medically qualified staff who are deemed experienced and competent at inserting PNCs by the PI and have been delegated this responsibility as per the PLACEMENT delegation log, are required to watch the Training presentation and read the PLACEMENT Trial SOP for the insertion of PNCs. This training must be documented on the PLACEMENT Training log. The PLACEMENT Delegation and Training logs will be monitored by the CTR.

12 Trial Procedures

All participants will be enrolled in the trial for approximately six months, from pre-operative screening to 6-month postoperative follow-up. During the inpatient phase there is a pre-operative baseline assessment and daily postoperative assessments up to five days following the operation. If a member of the research team is unable to collect patient reported outcomes (PROs) (e.g., over the weekend), a member of the clinical team may be permitted to collect this data. If a member of the clinical team is unable to retrospectively captured from information in the clinical notes. Should pain scores be routinely captured, but not using an 11-point scale, we will permit conversion of clinical pain scores (with a range of none (0) – severe (3)) as per published conversion methods (18).

During follow-up there are two assessments, which may be conducted either via telephone, email, post or in person at 3 months and 6 months post randomisation.

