12.1.5 Outcomes Collected at 30 Days

- Surgical site infection, as defined by CDC 2021 (55)
- Delayed **wound healing** of the surgical wound (defined as absence of complete epithelialisation of the wound)
- Residual limb surgery (revision or debridement)

Table 2 Schedule of enrolment, interventions, and assessments

Dat	а Туре	Source Data	Data type	Screening	Baseline/ Pre- operative assessment	At Operation	First 5 Post- operative days	30 days	At discharge	3 Month FU	6 Month FU	Freque ncy	By whom
1	Informed Consent	Consent form, documente d in medical notes	-	X								Once	Qualified practitioner with delegated responsibility
2	Eligibility Assessment	Eligibility form	-	X								Once	Qualified practitioner with delegated responsibility
3	Registration	Registratio n form	-		x							Once	Site research team
4	Demographics	CRF			X							Once	Site research team

Dat	а Туре	Source Data	Data type	Screening	Baseline/ Pre- operative assessment	At Operation	First 5 Post- operative days	30 days	At discharge	3 Month FU	6 Month FU	Freque ncy	By whom
5	Past surgical and medical history	Medical notes and CRF	(inc. smoking history, weightl, and type of diabetes mellitus)		x							Once	Site research team
6	Pre-operative pain	CRF	11-point NRS		x							Once	Participant reported
7	Pre-operative opioid and analgesic use	Medical notes			X							Once	Site Research team
8	Pre-operative blood results, including liver & renal function tests	Medical notes	Routine blood tests		X							Once	Site Research team

Data	а Туре	Source Data	Data type	Screening	Baseline/ Pre- operative assessment	At Operation	First 5 Post- operative days	30 days	At discharge	3 Month FU	6 Month FU	Freque ncy	By whom
9	Review of pre- operative resting 12-lead ECG	Medical notes	ECG		x							Once	Site Research team
10	(For participants of child-bearing potential) Review of pre- operative pregnancy test result	Medical notes	Pregnanc y test result		X							Once	Site Research team
11	Planned level of amputation	Medical notes			X							Once	Site Research team
12	Health services contact in previous 3 months	QRF	Client Service Receipt Inventory (CSRI)		x					X	x	Once	Participant reported / Site Research team

Data	а Туре	Source Data	Data type	Screening	Baseline/ Pre- operative assessment	At Operation	First 5 Post- operative days	30 days	At discharge	3 Month FU	6 Month FU	Freque ncy	By whom
13	Health-related Quality of Life	QRF	EQ-5D-5L and HADS		Х					x	x	Once	Participant reported

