Data	і Туре	Source Data	Data type	Screening	Baseline/ Pre- operative assessment	At Operation	First 5 Post- operative days	30 days	At discharge	3 Month FU	6 Month FU	Freque ncy	By whom
31	Phantom limb pain		11-point NRS							X	X	Once	Participant reported
32	Chronic stump pain		11-point NRS							Х	X	Once	Participant reported
33	Prosthesis fitting (inc. Time to achieve fitting)		SIGAM							Х	X	Once	Participant reported
34	Level of independence		SIGAM grading							x	x	Once	Participant reported
35	Resource Use (additional operations, consultations)	QRF						X		X	x	Once	Participant reported
36	Length of hospital stay	Medical notes							X		X	Once	Site Research team

Data	а Туре	Source Data	Data type	Screening	Baseline/ Pre- operative assessment	At Operation	First 5 Post- operative days	30 days	At discharge	3 Month FU	6 Month FU	Freque ncy	By whom
37	Hospital re- admissions										x	Once	Site Research team
38	MLLA of contralateral limb										X	Once	Site Research team
39	Mortality (Time, Cause)	Medical notes									X	Once	Site Research team
40	Adverse effects	Medical notes /CRF						As R	equired		L 	1	Site Research team
41	SAEs / SARs	Medical notes /CRF	SAE form					As	Required				Sit Research team
42	Withdrawals	Withdrawal form	-					As	Required				Site Research team and CTR

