12.2.2 Six-month Follow-up

At the 6 month follow up, all the PROs will be collected as per the 3 month follow up, and a medical note review will collect:

• Mortality, including cause of mortality

- Delayed wound healing of the surgical wound (defined as absence of complete epithelialisation of the wound)
- Residual limb surgery (revision or debridement)
- (For unilateral amputees) MLLA of contralateral limb
- Length of hospital stay (censored at 6 months in the unlikely event that the participant remains in hospital at 6-month follow-up), including re-admissions after discharge, used to calculate DAOH-90 and time spent in level 2 or 3 care.

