15.1 Main Analysis

For the statistical analysis of the primary outcome (proportion of 'successes' and 'failures' of pain control in the first 5 postoperative days for each participant, as defined in Section 14.3), we will use the intention-to-treat population and fit a multilevel logistic regression model, with the minimisation variables and condition (PAD or diabetes) as fixed-effect covariates and with random centre effects, to test for a difference between treatment arms at a 5% two-sided alpha level. Secondary outcomes will be analysed using similar multilevel regression models depending on the type of outcome (see Table 8) with the same covariate adjustments using the intention-to-treat principle. We will account for possible 'truncation by death' in sensitivity analyses. Additional secondary analyses considering the level of intervention fidelity will also be undertaken, including successful placement of the PNC, the PNC remaining in place for 5 days, and the local anaesthetic being infused within the dose and

rate ranges specified in the protocol for 5 days. All treatment effects will be reported as point estimates with 95% confidence intervals and p-values.

Table 8 Summary of Analysis for Secondary Outcomes

Outcome	Measure	Time frame	Analysis
Average pain	NRS	5d	Linear regression of median or mean (adjusted for baseline)
Overall satisfaction with analgesia	Likert scale	5d	Linear regression of transformed measure (if appropriate)
Total opioid use	Morphine equivalents	5d	Linear regression (adjusted for baseline)
Opioid side effects	Frequency and severity of symptoms	5d	Linear regression of transformed measure (if appropriate)
Surgical site infection	Proportion of people with infection	30d	Logistic regression
Delayed wound healing	Proportion of people with delay	30d, 6m	Logistic regression
Residual limb surgery	Proportion of people with surgery	30d, 6m	Logistic regression
Phantom limb pain	NRS	3m, 6m	Linear regression
Chronic stump pain	NRS	3m, 6m	Linear regression
Health utility/QoL	EQ-5D-5L	3m, 6m	Linear regression of transformed measure (adjusted for baseline)
Depression	HADS	3m, 6m	Linear regression of transformed measure (adjusted for baseline)
Prosthesis fitting	Proportion of people using prosthesis Time to achieve fitting	3m, 6m	Logistic regression Cox regression

Level of independence	SIGAM grading	3m, 6m	(Ordered) logistic regression, tabulation
independence			
Mortality	Proportion of people dead	6m	Logistic regression

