15.3 Cost Effectiveness Analysis

A within-trial economic evaluation will assess:

- 1. Resource use and costs associated with the use of PNC compared to no PNC in the postoperative period.
- Resource use and associated costs from baseline to six months post-amputation for PNC compared to no PNC.
- Cost-effectiveness measured in terms of a) the incremental cost for percentage increase in freedom from pain at five days and b) the incremental cost per quality adjusted life year (QALY) gain at six months, with trial outcomes reported in a cost consequence analysis.

The primary health economic analysis will adopt a UK NHS perspective at six months. A partial societal perspective considering participant costs and lost work, will also be considered. A health economic analysis plan will be developed with the evaluation reported according to the Consolidated Health Economic Evaluation Reporting Standards (CHEERS) statement (68).

Delivery costs associated with PNC (compared to no PNC) will be calculated from trial records (e.g., device costs, drugs). Using a current understanding of costing surgical trials (69), and data from our feasibility trial, a process map/pathway of care for the intervention and control group will be produced with the trial team, targeting efficiency of costing on key resource drivers (e.g., replacement equipment and staff time). Participant-level resource use for both PNC and no PNC groups will be collected using an adapted Client Service Receipt Inventory (CSRI) developed to capture subsequent

resources to the NHS, patient and society based on good practice (70), and other surgical trial contexts (71). Data collected from trial report forms alongside expert clinical and participant opinion will be used to calculate resource use with relevant published unit costs or local records/literature sources used to value resource use in pound sterling. A comprehensive summary of costs to UK NHS will be produced.

The primary economic outcome will be QALY gain/lost at six months derived from participant reported Health-Related QoL. Utility scores will be obtained using the EQ-5D-5L instrument. EQ-5D-5L will be administered at baseline, and 3-month and 6-month follow-ups within the CSRI. No discounting will be undertaken as the trial horizon does not exceed 12 months.

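### The 6-month note review may be done anywhere from 4 to 8 months with no common cut-off, so the 6-month event proportions mix unequal exposure; a fixed 3-month cost recall can likewise leave gaps or overlaps

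*Protocol*

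**What the plan says.** Section 12.2 sets the windows: "Follow-up assessments will be carried out at 3 months (+/- 1 month window) and 6 months (+/- 2month window". The 3-month contact may thus fall at 2 to 4 months and the 6-month contact at 4 to 8 months. The opening of section 12 counts them from randomisation ("3 months and 6 months post randomisation"). Section 12.2 also lets clinical information from a routine outpatient visit inside the window serve as the follow-up assessment.

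Section 12.2.2 says that at the 6-month follow-up "a medical note review will collect" mortality, delayed wound healing, residual limb surgery, contralateral amputation and length of stay. No earliest date is given. A horizon is stated for one item only: "Length of hospital stay (censored at 6 months in the unlikely event that the participant remains in hospital at 6-month follow-up". Table 2 schedules these items, and re-admissions, at the 6-month follow-up with frequency once. It asks for timing only for death: "Mortality (Time, Cause".

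Table 8 (section 15.1) analyses residual limb surgery, delayed wound healing, re-admission, contralateral amputation and mortality ("Proportion of people dead") as proportions at 6 months by logistic regression. A Cox model is also listed for time to death and for time to discharge.

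For costs, row 12 of Table 2 is labelled "Health services contact in previous 3 months" and is ticked at baseline, 3 months and 6 months. The economic horizon in section 15.3 is: "Resource use and associated costs from baseline to six months post-amputation for PNC compared to no PNC".

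**The concern.** A proportion at 6 months needs the same 6 months of observation for everyone. A protocol-compliant review at month 4 holds nothing on months 4 to 6, and no later analysis plan can recover what was not collected. A review at month 8 can include events after month 6 unless they are dated and cut, and the protocol asks for a date only for death. Delayed wound healing is a state rather than an event, so an early look finds more wounds still open and over-counts it.

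The same windows act on costs. Two 3-month recalls cover a 6-month horizon exactly only when the contacts fall at exactly 3 and 6 months. Otherwise some weeks are not asked about, are asked about twice, or lie outside the horizon. The six-month NHS cost total feeds the primary economic analysis.

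**Working it through.** **The plan's own figures.** The protocol gives no calculation on this point and no 6-month event rates. Its one stated calculation, the sample size in section 14.3, does reproduce: 61.7% against 61.7% × 1.2 = 74.04%, two-sided 5% alpha and 90% power give 299 per arm, and 598 / 0.92 = 650. It concerns the first five days and does not depend on the follow-up windows.

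**Windows.** 3 ± 1 gives 2 to 4 months; 6 ± 2 gives 4 to 8 months. The interval between the two contacts can be 4 − 4 = 0 up to 8 − 2 = 6 months. Exposure at the note review can differ two-fold (4 against 8 months).

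**Event proportions.** Let P be the true 6-month proportion. This is an assumption, shown as a range. With a constant hazard (also assumed), the proportion seen at t months is 1 − (1 − P)^(t/6).

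| True P at 6 months | Read at 4 months | Read at 8 months, no cut-off |
|---|---|---|
| 10% | 6.8% | 13.1% |
| 20% | 13.8% | 25.7% |
| 30% | 21.2% | 37.8% |

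If events cluster soon after surgery, these differences shrink.

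**Cost recall.** With contacts at a and b months, the recalls cover [a − 3, a] and [b − 3, b]. Set against the horizon [0, 6]:

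| Contacts (a, b) | Months uncovered | Months counted twice | Months included after month 6 |
|---|---|---|---|
| 3, 6 | 0 | 0 | 0 |
| 2, 8 | 3 | 0 | 2 |
| 3, 8 | 2 | 0 | 2 |
| 3, 4 | 2 | 2 | 0 |
| 2, 4 | 2 | 1 | 0 |
| 4, 4 | 3 | 3 | 0 |

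A contact at month 2 also reaches back one month before surgery.

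**Typical size.** Suppose both contacts are spread evenly over their windows (an assumption). The interval b − a then averages 3 months, and the mean gap between the two recalls and their mean overlap are each about 0.5 month. The horizon can also be uncovered at its two ends. A first contact after month 3 leaves a − 3 uncovered at the start, on average ½ × 0.5 = 0.25 month. A second contact before month 6 leaves 6 − b uncovered at the end, on average ½ × 1 = 0.5 month. The mean total uncovered is 0.54 + 0.25 + 0.5, or about 1.3 of 6 months.

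**Timetable.** Section 25 has recruitment to month 30 and last follow-up at month 36; section 19 ends follow-up 6 months after the last participant completes treatment. A permitted 8-month contact for the last recruit would fall at month 38. Both passages point to a 6-month horizon that the window does not enforce.

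**The case against.** Several safeguards are in the text, and they stand. Time of death is recorded and a Cox model is listed, so the time-to-event analysis of mortality copes with unequal follow-up; only the logistic analysis is exposed. Length of stay is censored at 6 months, and days alive and out of hospital at 90 days ends before the earliest permitted 6-month contact.

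On costs, the 3-month recall at follow-up rests on one row label in Table 2. Section 12.2.1 describes the follow-up questionnaire without a recall period, section 15.3 calls the instrument adapted, and row 35 of Table 2 adds a resource-use entry at 30 days. Section 16.4 gives clinically trained research staff access to hospital and GP records for resource use, and section 15.3 foresees multiple imputation and a separate health economic plan. Gaps and double counting are therefore possible rather than certain. However, no rule says how the sources combine, and records would not readily show participant costs or lost work.

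A reader might infer more than the documents support:

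- **That events are counted twice.** A yes/no outcome cannot be; only costs can.
- **That every listed outcome is under-counted by an early review.** Unhealed wounds are over-counted.
- **That unknown later events are scored as absent by rule.** The protocol states no such rule. A later look at the notes is not forbidden, but none is required.
- **That the treatment comparison is biased.** Nothing suggests that contact timing differs by arm. The open-label design means equal timing is not guaranteed, but a difference is not shown.

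The wide contact window also has a purpose. Section 17.1 reports that fewer than 40% of living feasibility participants gave 6-month data, so narrowing it could cost response.

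**Conclusion.** The point holds for the note review and, with more reservation, for the cost recall. As written, a compliant review can be two months early or two months late. The affected outcomes are residual limb surgery, re-admission, contralateral amputation, the logistic analysis of mortality and, as a state read at differing times, delayed wound healing. At the window limits, and with a constant hazard, a true 20% would be misread by about 6 percentage points either way (20 − 13.8 = 6.2; 25.7 − 20 = 5.7). The event rate and the hazard shape are assumptions, not protocol figures.

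For costs, up to 3 of 6 months uncovered and up to 3 counted twice are the extremes of the permitted windows. Evenly spread contacts would give a gap and an overlap between recalls averaging about 0.5 month each. This assumes that the row 12 label is the recall actually used and that records fill nothing.

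The consequence is mainly misclassification, noise and mis-stated 6-month rates and costs. These are secondary and economic outcomes; the primary outcome and the sample size are untouched. The change is worth making because an analysis plan can cut a late review if events are dated, but cannot complete an early one.

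**What to change.** 1. Separate the note review from the questionnaire contact. Do it on or after day 183 for every participant.
2. Record the date of each event, including the date of wound healing where available, and count events only to day 183.
3. Word the resource-use recall as *since your operation* at 3 months and *since your last questionnaire* at 6 months, or since the operation if the 3-month questionnaire was missed. Record completion dates, and truncate or scale costs to the 6-month horizon.
4. Leave the questionnaire windows unchanged, to protect response.

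The cost is wording in the visit schedule, date fields on the form and one questionnaire stem, with no new participant contacts. Some participants face a slightly longer recall, and the last note reviews cannot be done before month 36.

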14.2 Blinding

The PLACEMENT trial does not use blinding.

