Attrition in the PLACEMENT feasibility trial was high; less than 40% of alive participants provided outcome data at six months (50). Research on how to improve follow-up, particularly in this cohort of participants, is essential given the importance the PPI focus group, and the team who developed the amputation Core Outcome Set (44), placed on long-term outcomes. Assessing tools aimed at improving follow-up aligns with the Prioritising Recruitment in Randomised Trials study (PrioRiTy II) priorities (73), including research question number 4: "what are the best ways to encourage trial participants to complete the tasks (e.g., attend follow-up visits, complete questionnaires) required by the trial?".

We will conduct a study within a trial (SWAT) which will assess the presentation of video information at the point of discharge on follow up rates. This will include information about how the follow-up is organised and undertaken, and prompt discussion around its practicalities. This will be shown to the participant alongside a follow up information leaflet.

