17.2 Methods

At the time of randomisation (to PNC no PNC), participants will be also randomised (1:1) to the SWAT. Every alive participant will be reviewed by the research team at day 7 (+/-2 days) to confirm capacity to consent, and those randomised to participate in the SWAT will be shown a short video, created by

the TMG, about what the follow-up will entail, when it will be, and how long it will take. The video will also be shown to those participants randomised to the SWAT on the day of discharge, if possible. All participants will be given a leaflet regarding their follow-up, and a chance to ask any questions regarding it. The video will contain the same information as the follow up information leaflet. Our primary hypothesis is that those shown the video will engage better with follow-up than those only given the information leaflet alone.

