17.3 Results

The primary outcome of the SWAT will be successful completion of 6-month follow-up data capture. Completion rates will be presented as point estimates of the difference in rates alongside 95% confidence intervals.

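### Follow-up contact effort is discretionary and nothing keeps the caller unaware of SWAT allocation, yet the SWAT's primary outcome is follow-up completion, which depends on that effort and is loosely defined

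*Protocol*

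**What the plan says.** Section 12.2 describes contact at 3 and 6 months by telephone or email, using both where possible. On the amount of effort it says: "Around 3 attempts will be made to contact the participant at each follow-up". A relative or carer is a permitted alternative. The last step is also permitted rather than required: "If all contact attempts are unsuccessful, a questionnaire booklet may be posted to the participant for them to complete and return". Questionnaires may be completed in person at a routine visit that falls within the window, and clinical information from that visit may be used. The 6-month window is plus or minus 2 months.

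Section 12.2.2 gives the 6-month follow-up two parts: the participant-reported outcomes, and items that "a medical note review will collect" (mortality, wound healing, residual limb surgery, contralateral amputation, length of stay).

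Section 17.2 randomises participants 1:1 to the SWAT. All receive a leaflet, and "those randomised to participate in the SWAT will be shown a short video". The stated hypothesis is that those shown the video will engage better with follow-up. Section 17.3 says: "The primary outcome of the SWAT will be successful completion of 6-month follow-up data capture", reported as a difference in rates with a 95% confidence interval. The motive, in section 17.1, is that in the feasibility trial "less than 40% of alive participants provided outcome data at six months".

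Section 14.2 says: "The PLACEMENT trial does not use blinding". Section 17 adds no concealment for the SWAT.

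**The concern.** In most trials, some looseness in how hard staff chase a questionnaire is tolerable. Here the SWAT measures whether the chase succeeded. If the person making contact knows who saw the video and tries a little harder, or a little less hard, for that group, the difference in completion mixes the effect of the video with the effect of the effort. The protocol has no rule that equalises effort, no concealment step and no stated log of attempts from which a reader could later check.

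A second, smaller weakness is that 17.3 does not say which parts of 6-month data capture count. The note review and clinical information from a routine visit need no engagement from the participant, while the hypothesis is about engagement.

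The same discretion applies by perineural catheter (PNC) arm in the open-label main trial. The participant-reported outcomes at 3 and 6 months (phantom limb pain, stump pain, EQ-5D-5L, HADS) could therefore be missing to different degrees in the two arms.

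**Working it through.** **The plan's own figures.** The protocol gives no SWAT sample size, target difference or power, so there is no SWAT figure to reproduce. The main-trial calculation in 14.3 does reproduce: 61.7% versus 61.7% × 1.2 = 74.04%, two-sided 5% alpha and 90% power give 299 per arm, and 598 / 0.92 = 650. It is not affected by this point.

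**Assumptions, none given by the protocol**
- Completion is 40% after three attempts. This is anchored on the feasibility figure of under 40% in 17.1, whose contact procedure is not described.
- There are 200 to 325 living SWAT participants per group, that is, 400 to 650 in total. The upper end is all 650; the SWAT is optional, so the number could be lower still.
- The video has no effect.

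**Model A: independent attempts, equal success for everyone**
- Success per attempt: q = 1 − (1 − 0.40)^(1/3) = 0.157.
- Completion after four attempts: 1 − (1 − 0.157)^4 = 49.4%.
- One extra attempt throughout one group: 0.60 × 0.157 = 9.4 points. For base completion of 30% to 70% this ranges from 7.8 to 10.5 points.

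**Model B: half of survivors cannot be reached**
- 40% overall means 80% of the reachable half, so q = 1 − (1 − 0.80)^(1/3) = 0.415.
- One extra attempt throughout one group: 0.5 × 0.20 × 0.415 = 4.2 points.

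**Precision.** The standard error of the difference is √(2 × 0.4 × 0.6 / n). This is 4.9 points at n = 200 and 3.8 points at n = 325, so the 95% interval half-width is 9.6 to 7.5 points.

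**Shift, and the chance that the interval excludes zero in favour of the video when it has no effect (nominal 2.5%)**

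| Share of one group given an extra attempt | Model A shift | Model A chance | Model B shift | Model B chance |
|---|---|---|---|---|
| All | 9.4 points | 48% to 68% | 4.2 points | 13% to 19% |
| Half | 4.7 points | 16% to 23% | 2.1 points | 6% to 8% |
| One tenth | 0.9 points | about 4% | 0.4 points | about 3% |

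Each chance is 1 − Φ(1.96 − d / SE), where d is the shift and SE = √[(0.4 × 0.6 + p(1 − p)) / n] with p = 0.4 + d, for n from 200 to 325.

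**Booklet.** Suppose it is posted to 20 percentage points more of the non-responders in one group, with an assumed return of 10% to 30%. The shift is 0.60 × 0.20 × 0.10 = 1.2 points to 0.60 × 0.20 × 0.30 = 3.6 points.

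With equal effort in both groups, the bias from this source is zero.

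**Definition of the outcome.** Section 17.2 speaks of engagement and 17.1 of participants providing data. Section 12.2.2 puts both participant-reported outcomes and note review under the 6-month follow-up, and 17.3 refers to data capture without choosing between them. Counting the note review would be expected to dilute a real difference rather than create a false one. It is a clarity defect, separate from the effort question.

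**The case against.** A reader might infer that the staff who show the video also make the 6-month calls and know the allocation. The protocol does not say so. Section 17.2 has the research team review participants at day 7, and section 10.1 has a member of the research team make the follow-up contact. Section 9.4, however, uses the same term for a group separate from the sites, and no section says that the caller knows who saw a video months before. The blinding statement in 14.2 is about the trial in general. What stands is narrower: nothing prevents the caller from knowing.

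A reader might also take the spread of completion across two, three and four attempts as the size of the bias. It is not. The open wording applies to everyone alike, and variation unrelated to allocation does not bias the difference. Bias needs a systematic gap between groups, and the protocol gives no evidence that there will be one.

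The largest figures need a full extra attempt across a whole group together with independent, equally successful attempts, an assumption poorly suited to a population with many hard-to-reach people. Model B more than halves the shift.

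On the outcome wording, 17.1 and 17.2 suggest that participant-provided data are meant. That is the likely intention, but 17.3 does not say it.

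**Conclusion.** The concern holds as an uncontrolled risk of bias to the SWAT. Discretionary effort acts directly on its primary outcome, nothing equalises that effort or conceals the allocation from the caller, and the outcome is worded loosely enough for note review to count in part.

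Under the stated assumptions the size runs from 1 point or less, if a tenth of one group receives an extra attempt, to about 4 to 9 points if the whole group does. Only the top of that range is comparable with the SWAT's own interval half-width of 7.5 to 9.6 points. The result depends on the assumed 40% base, the assumed number of survivors taking part and the assumed reachability.

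The risk of differential missingness by PNC arm in the 3- and 6-month patient-reported outcomes is lesser and unquantified. The primary pain outcome, collected over the first five postoperative days, is unaffected. This is a cheap improvement rather than an error that threatens the trial's main conclusion.

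**What to change.** In section 12.2, set one common sequence for every participant at each follow-up:
- a minimum of three telephone or email attempts;
- then the alternative contact, where consented;
- then a booklet that will be posted to every remaining non-responder.

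Keep in-person completion available to all. A minimum is better than an exact number, because a cap would work against the section's own aim of maximising response.

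Keep SWAT allocation from whoever makes the contact, where feasible. Log the number of attempts and the mode of completion, and report both by SWAT group and by PNC arm.

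In section 17.3, define the SWAT primary outcome as the participant's own 6-month questionnaire set completed within the window, excluding note review.

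The cost is a few sentences, a short contact log, some postage and slightly less flexibility for sites. A minimum does not by itself make effort equal above three attempts, so the concealment and the log are needed alongside it.
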